Statistical analysis plan and sample size calculation

Official Title:

The Effect of Chronic Nitrate Supplementation on Acute Mountain Sickness and Exercise Performance in Hypoxia

NCT number

NCT03101904

Document Date

15/10/2015

High-altitude headache

RM ANOVA

2x4 RM ANOVA = Total of 8 repeated measures

	Av correlation		Meaningful difference	Effect size		Sample size
	Calculated	Table		Calculated	Table	
Hypoxia	0.6	Strong = 0.5	14	0.7	Large = 0.57	14
			10	0.5	Medium = 0.35	23
All data	0.2	Weak = 0.3	14	0.7	Large = 0.49	16
			10	0.5	Large = 0.49	16
4 measures	0.4	Weak = 0.3	10	0.7	Large = 0.49	16

Calculations (4 measures)

Average correlation

		Hypoxic			Normoxic
		4 h	6 h	8 h	8 h
Hypoxic	4 h	1	0.4	0.4	
	6 h		1	0.9	
	8 h			1	-0.3
Normoxic	8 h				1

Average correlation = 0.4

Effect size

Meaningful difference = 10

SD of difference (4-6 h in hypoxia) = 18

Cohen's D = 0.55

Conversion to RM ANOVA effect size = $0.55 / (\text{SQRT}(1-0.4)) = 0.7$

(Stevens, 2002)

A sample size estimation for this analysis indicated that 16 participants were needed to produce an 80% chance of obtaining statistical significance at the 0.05 level (5), based on a minimum important difference of 10 mm (2), a standard deviation of the difference of 18 mm, and an estimated average correlation of 0.4 (data from (3)).

Time to exhaustion

t tests – Means: Difference between two dependent means (matched pairs)

Analysis: A priori: Compute required sample size

Input:	Tail(s)	=	Two
	Effect size dz	=	0.9090909
	α err prob	=	0.05
	Power (1- β err prob)	=	0.8
Output:	Noncentrality parameter δ	=	3.1491833
	Critical t	=	2.2009852
	Df	=	11
	Total sample size	=	12
	Actual power	=	0.8174086

The effect of nitrate supplementation on maximal exercise performance (TTE) was determined by paired samples t-test. A sample size estimation for this analysis indicated that 12 participants were needed to produce an 80% chance of obtaining statistical significance at the 0.05 level for a two-tailed design (1), based on a minimum important difference of 30 seconds and a standard deviation of the difference of 33 seconds (data from (4)). Given the smaller required sample size for this analysis, only 15 participants completed the TTE component of the study.

References

1. **Bland M.** *Determination of sample size*. 4th ed. Oxford: Oxford University Press, 2015.

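### The headache sample size is for an eight-level omnibus test whose SD and correlations are not nitrate-minus-control quantities, so its 80% for 10 mm is not power for a nitrate effect

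*SAP*

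**What the plan says.** The section on high-altitude headache opens its RM ANOVA calculation with "2x4 RM ANOVA = Total of 8 repeated measures". It does not label the two factors. Treatment by time/condition is inferred from the trial title and from the four measures in the correlation matrix: hypoxic 4, 6 and 8 h, and normoxic 8 h.

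The effect size is built from a 10 mm meaningful difference and "SD of difference (4-6 h in hypoxia) = 18". Their ratio, 0.55, is divided by the square root of 1 minus the correlation, using "Average correlation = 0.4", to give 0.7. The table row adopted has effect size 0.49 and 16 participants. The other rows print 14 participants (effect size 0.57), 23 (0.35) and again 16 (0.49).

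The summary sentence reads "A sample size estimation for this analysis indicated that 16 participants were needed" and attaches 80% power, the 0.05 level, 10 mm, 18 mm and 0.4. It calls the 18 mm simply the SD of the difference and no longer says that it belongs to the 4 to 6 h change in hypoxia.

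The section on time to exhaustion (TTE) is explicit by comparison: "The effect of nitrate supplementation on maximal exercise performance (TTE) was determined by paired samples t-test".

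**The concern.** The trial asks whether nitrate changes headache. Folding a 2x4 design into eight repeated measures gives a test of whether any of the eight means differ. Headache that rises in hypoxia, equally under nitrate and control, counts towards significance in that test.

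The inputs do not bring the calculation back to nitrate. The SD is for a change between two times, and the correlations are between times and between hypoxia and normoxia. The 10 mm could serve as a nitrate target, but no contrast, SD or correlation ties it to one.

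A reader will still take the 80% as the chance of detecting a 10 mm nitrate effect. That matters most for a null headache result, which would look better supported than the calculation allows.

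**Working it through.** **1. Reproducing the plan's sizes.** Test: multivariate repeated-measures omnibus, noncentral F with df k-1 and n-k+1, noncentrality n·k·f², alpha 0.05. Here f is the printed table effect size. Smallest n for at least 80% power:

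| Levels k | f = 0.57 | f = 0.35 | f = 0.49 |
|---|---|---|---|
| SAP prints | 14 | 23 | 16 |
| 8 | 14 | 23 | 16 |
| 7 | 14 | 23 | 16 |
| 4 | 13 | 27 | 16 |
| 2 | 15 | 35 | 19 |

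Of k = 2 to 10, only 7 and 8 give all three sizes, and the SAP says 8. The adopted n=16 alone fits any k from 4 to 9. With k=8 and f=0.49, power at n=16 is 0.83. A two-level comparison in the same framework would have needed 19.

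**2. What makes that test significant.** Assumption: the plan's 18 mm and 0.4 are common to all eight scores.
- Score SD = 18/√(2 × 0.6) = 16.43 mm.
- Error SD = 16.43 × √0.6 = 12.73 mm.

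*No nitrate effect.* Let a hypoxia effect of h mm act equally in both arms, so that each arm has means (0, h, h, h). The SD of the eight means is 0.433h, and f is that SD divided by 12.73.

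| h (mm) | f | Power, k=8, n=16 |
|---|---|---|
| 10 | 0.34 | 48% |
| 14.4 | 0.49 | 83% |
| 20 | 0.68 | 99% |

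*Nitrate effect only.* A 10 mm effect at all four measures gives an SD of the means of 5, f = 5/12.73 = 0.39 and power 62% (20 needed for 80%). A 10 mm effect at the three hypoxic measures only gives 59%. So even within the omnibus test, 10 mm of nitrate effect does not correspond to the adopted f of 0.49.

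**3. Power of n=16 for a direct nitrate contrast of 10 mm.** Two-sided paired t-test, alpha 0.05. Assumption: 18 mm is the SD of the nitrate-minus-control difference at each time, with correlation r between the differences at different times. The SAP gives neither.
- Single time point: dz = 10/18 = 0.556.
- Mean of three hypoxic measures: SD = 18 × √((1 + 2r)/3).
- Mean of all four measures: SD = 18 × √((1 + 3r)/4).

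| Contrast | r | Contrast SD (mm) | Power at n=16 | n for 80% |
|---|---|---|---|---|
| Single time | – | 18.0 | 55% | 28 |
| Mean of three | 0 | 10.4 | 95% | 11 |
| Mean of three | 0.4 | 13.9 | 76% | 18 |
| Mean of three | 0.4, 0.4, 0.9 | 15.2 | 69% | 21 |
| Mean of three | 1 | 18.0 | 55% | 28 |
| Mean of four, 10 mm at each | 0.4 | 13.35 | 80% | 17 |
| Mean of four, 10 mm in hypoxia and none in normoxia | 0.4 | 13.35 | 56% | – |

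In the last row the averaged effect is 10 × 3/4 = 7.5 mm. In the row above it, power is 79.96%, just under 80%, hence n = 17.

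The common-correlation model of step 2 implies r = 0 between differences, and so the 95% row for the mean of three.

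**4. The break-even SD.** Power of 80% at n=16 needs dz = 0.749. For 10 mm, the SD of the chosen nitrate contrast can be at most 10/0.749, about 13.3 mm.

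**The case against.** The strongest case for the plan has four parts.

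- **A natural nitrate test comes close to the stated power.** The treatment main effect of the 2x4 ANOVA averages four measures. With 18 mm at each time and differences correlating 0.4, n=16 gives essentially 80% for 10 mm. This stands as one scenario. It needs the full 10 mm in normoxia as well (56% if there is no effect there), and a correlation between scores has to be borrowed for differences. The plan makes neither argument.
- **The alternative figures rest on assumptions.** They run from 55% to 95% and show no direction of error. The plan's own correlations, which include 0.9 and -0.3, do not fit the common correlation used for the 48%, 83% and 99%. This stands, and those figures are illustrative. It is also the point: the plan does not contain what is needed to state nitrate power.
- **The omnibus reading is partly inferred.** The source table cannot be seen, and k=7 fits as well as k=8. The SAP's own count of eight and three matched sizes support the reading, and seven levels would be no more specific to nitrate.
- **The sentence claims power for the analysis, and the protocol may name the tested effect.** Both are fair. Naming a test elsewhere would not turn a calculation from between-time quantities into power for that test.

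Recalculation cannot change recruitment either, since the SAP already reports how many participants completed the TTE component. That limits the consequence to how the headache result is read.

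**Conclusion.** The concern holds. The 80% attached to 16 participants and 10 mm is the power of an omnibus test, built on an SD and correlations that describe changes over time and condition. It is not the chance of detecting a nitrate effect on headache. The reproduction of 14, 23 and 16 supports this without further assumptions about the data.

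The size of the discrepancy does depend on assumptions. With 18 mm as the difference SD at each time, nitrate power at n=16 is 55% at a single time point and 55% to 95% for the mean of three hypoxic measures. It reaches 80% only if the contrast SD is no more than about 13.3 mm, a value the SAP neither states nor justifies.

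This is a planning fault that should be fixed. It does not show that 16 participants are too few, and it does not affect the validity of the ANOVA's treatment and interaction tests.

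**What to change.** Name one nitrate test for headache. Candidates are the 1-df nitrate-minus-control contrast on mean hypoxic headache, the treatment main effect, or the treatment-by-time interaction of the 2x4 ANOVA. Label the two factors.

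Replace the 80% statement with the power of n=16 for that test at 10 mm. Tabulate it over a stated range of difference SD and of correlation between differences, marked as assumptions because the SAP gives neither. In the summary sentence, say that the 18 mm is the SD of the 4 to 6 h change in hypoxia.

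The cost is a change of wording and one recalculation, with no new data. The single 80% becomes a range that may lie above or below it.

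### Must the SAP state a non-sphericity correction for the headache RM ANOVA?

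*SAP*

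**What the plan says.** Under High-altitude headache the SAP gives the analysis as "2x4 RM ANOVA = Total of 8 repeated measures". It does not name the two factors or their levels. The sample-size paragraph sets the 0.05 level and 80% power and arrives at 16 participants, using a 10 mm difference and "a standard deviation of the difference of 18 mm, and an estimated average correlation of 0.4", both attributed to an earlier study.

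The Average correlation table lists 0.4 (4 h with 6 h), 0.4 (4 h with 8 h) and 0.9 (6 h with 8 h) in hypoxia, and -0.3 between hypoxic 8 h and normoxic 8 h. The other cells that involve the normoxic measure are blank. These are summarised as "Average correlation = 0.4". The only SD supplied is "SD of difference (4-6 h in hypoxia) = 18" (mm); no SD is given for a single time point.

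The SAP does not mention sphericity, an epsilon correction, a multivariate test or a mixed model. Nor does it say that uncorrected degrees of freedom will be used.

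**The concern.** A univariate repeated-measures F test with more than one numerator degree of freedom holds its nominal level only if all pairwise differences between levels have the same variance. The planning correlations point the other way: 6 h and 8 h move almost together, while 4 h is only moderately related to either. A plan that prints such correlations and then names an ordinary RM ANOVA appears to overlook an assumption that its own figures contradict.

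Two things would be at stake. With uncorrected degrees of freedom, the multi-df tests could reject too often under the null. And because the choice is not written down, it could be made after the data are seen, when it might decide whether a borderline multi-df test counts as significant. Power is a secondary worry, since a correction lowers the power of 16 participants for those tests.

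**Working it through.** **Reproducing the SAP's own figures**
- Average correlation: (0.4 + 0.4 + 0.9 - 0.3)/4 = 0.35, printed as 0.4.
- Cohen's d: 10/18 = 0.556, printed as 0.55.
- RM ANOVA effect size: 0.55/sqrt(1 - 0.4) = 0.71, printed as 0.7. The tabled value used is 0.49.
- Sample size, by noncentral F under sphericity with f = 0.49, degrees of freedom k - 1 and (k - 1)(n - 1), and noncentrality n·k·f²: k = 3 needs 15, k = 4 needs 13, k = 8 needs 9. Only k = 3 comes close to the SAP's 16. There the noncentrality is 16 × 3 × 0.49² = 11.52 and the power 0.83.

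**Are the three hypoxic measures spherical?**
Assume equal SDs at the three times.
- SD per measure: 18/sqrt(2(1 - 0.4)) = 16.4 mm.
- SD of the 4-8 h difference: 16.4 × sqrt(1.2) = 18.0 mm.
- SD of the 6-8 h difference: 16.4 × sqrt(2(1 - 0.9)) = 16.4 × sqrt(0.2) = 7.3 mm.
- The variances of the differences are in the ratio 1.2 : 1.2 : 0.2, a six-fold spread.

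Unequal SDs do not rescue this. Let a, b, c be the SDs at 4, 6 and 8 h. Equal variances for 4-6 h and 4-8 h require b = c or b + c = 0.8a.
- If b = c, equality with 6-8 h requires a² - 0.8ab + 0.8b² = 0, which has no real root.
- If b + c = 0.8a with a = 1, it requires 2.8b² - 2.24b - 0.36 = 0. One SD is then 0.937 and the other -0.137, which is impossible.

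**Size of the effect on a three-level time test (equal SDs, n = 16)**
- The orthonormal contrast of 6 h with 8 h has variance 1 - 0.9 = 0.1.
- The contrast of 4 h with the mean of the other two has variance (4 + 1 + 1 - 1.6 - 1.6 + 1.8)/6 = 0.767. The two contrasts are uncorrelated.
- Epsilon = (0.1 + 0.767)²/(2(0.1² + 0.767²)) = 0.63.
- Simulated type I error is 7.4% with ordinary degrees of freedom and 5.0% with Greenhouse-Geisser.
- With the 6 h and 8 h SDs assumed at 0.5 to 2 times the 4 h SD, the uncorrected error is 6.1% to 8.3%.
- Four-level versions, with the missing correlations assumed, give 6.8% to 8.3%.

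**Does this reach a comparison of supplements?**
Assume the factors are supplement (2 levels) and time (4 levels).
- Supplement main effect: 1 degree of freedom, so sphericity does not arise.
- Supplement by time: what matters is the covariance of the between-supplement differences, 2R - 2C. Here R is the within-session matrix, in correlation units, and C the cross-session matrix, on which the SAP has no information. If C = 0.5R, the differences have covariance R and the error is 7.4%. If C = R - 0.1I, they have covariance 0.2I, which is spherical, and the error is 5.0%. Both are admissible.
- Time main effect: the inflation above applies if ordinary degrees of freedom are used.

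**The case for a change.** The strongest case for acting is that setting the degrees of freedom of an F test is the SAP's business, that the departure from sphericity is visible in its own table, and that one sentence would close the gap. The first two points stand: the omission is real, and the printed correlations exclude sphericity. The third concerns cost and does not establish a defect.

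The link to this trial is weaker than it looks. The correlations are one-decimal estimates from an earlier study, used only for sizing. The SAP does not say that this trial's four levels include 4, 6 and 8 h. Its one printed set of four measures mixes three hypoxic times with a normoxic one, which is not a simple time factor. The 7.4% therefore describes a three-level proxy.

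The power argument also falls short. Under the same assumptions and an epsilon of 0.63, power at 16 drops from 0.83 to 0.68 for three levels and from 0.90 to 0.76 for four. But the four-level starting point is not the SAP's calculation, since k = 4 would need only 13, and most of the fourth level's correlations are blank. How the tabled 0.49 enters the noncentrality is also an assumption. This is too thin a basis for telling the sponsor to restate the power of N = 16.

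The worry about a choice made after seeing the data keeps some force for supplement by time. It is limited, because correcting multi-df within-subject tests is ordinary practice and standard software offers it.

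**Conclusion.** No change follows. The SAP leaves a routine analysis option unwritten; it states nothing wrong on this point and contradicts nothing. If this trial's time factor behaved like the three borrowed measures, with roughly equal SDs, 16 participants and no correction, the time main effect would be tested at about 7.4% instead of 5%, an excess of 2.4 percentage points. That test does not compare supplements. The 1-df supplement effect keeps its level, and inflation of supplement by time is possible but not established (5.0% to 7.4% in two equally admissible scenarios). An analyst meeting data of this kind would be expected to apply Greenhouse-Geisser or an equivalent, which restores about 5.0%. A sentence saying so would be harmless tidying, but no conclusion about nitrate has been shown to depend on it.

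This rests on reading the unnamed factors as supplement and time. The type I error figures also rest on the assumed SDs and, for four levels, on assumed correlations.

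### If the headache ANOVA's four levels are hypoxic 4, 6 and 8 h plus normoxic 8 h, its omnibus tests do not isolate the nitrate effect in hypoxia; one pre-specified hypoxic contrast would

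*SAP*

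**What the plan says.** Under High-altitude headache, the SAP gives the analysis as "2x4 RM ANOVA = Total of 8 repeated measures". It does not name the two factors. That the two-level factor is nitrate against a comparator (called placebo here) follows from the title and the layout.

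The calculation it adopts is the four-measures one. The correlation table there has four entries: hypoxic 4 h, 6 h and 8 h, and normoxic 8 h. It prints 0.4, 0.4 and 0.9 among the hypoxic hours and -0.3 between hypoxic and normoxic 8 h. The other two normoxic cells are blank. The summary is "Average correlation = 0.4". The spread used is "SD of difference (4-6 h in hypoxia) = 18", and the minimum important difference is 10 mm. The text attributes these data to an earlier study (SAP reference 3).

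The SAP then states: "A sample size estimation for this analysis indicated that 16 participants were needed". It does not say whether the 80% power belongs to a main effect, an interaction or a contrast. The Time to exhaustion section, by comparison, names both the nitrate effect and its test, a paired t-test.

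**The concern.** A factor made of three hypoxic hours and one normoxic hour is neither a time course nor a comparison of oxygen conditions, because normoxia appears at one hour only. The title asks about nitrate and mountain sickness in hypoxia, and neither omnibus test answers that directly:

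- The supplement main effect gives the normoxic score the same weight as each hypoxic hour. If nitrate does nothing to headache in normoxia, the estimate is pulled towards zero.
- The supplement-by-level interaction spreads 3 df over change with time and difference in oxygen condition. A significant result would not show which of them is responsible, and a nitrate effect that is constant across the hypoxic hours appears in it only as a departure from the normoxic level.

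At stake are a nitrate effect reported smaller than it is in hypoxia, an interaction that cannot be interpreted, and a choice between tests left open until the results are known.

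**Working it through.** **The plan's own figures.** The average correlation is (0.4 + 0.4 + 0.9 - 0.3)/4 = 0.35, printed as 0.4. The hypoxic average is (0.4 + 0.4 + 0.9)/3 = 0.57, printed as 0.6. The effect size is 10/18 = 0.556, and 0.55/√(1 - 0.4) = 0.71, printed as 0.7. These reproduce. The 16 does not follow directly. A one-way repeated-measures F test with the tabled 0.49, 80% power and sphericity needs 13 for four measures and 9 for eight. Four measures with a sphericity epsilon of 0.75 give 16, but the SAP states no such correction. The point below concerns what the test estimates and does not depend on how 16 was reached.

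**Assumptions for the check.** The levels are hypoxic 4, 6, 8 h and normoxic 8 h; n = 16; two-sided 0.05. The nitrate-placebo difference is 10 mm at each hypoxic hour and 0 in normoxia. Its SD is 18 mm at each hypoxic hour and 3 to 18 mm in normoxia. Correlations between the differences are either as printed (blank cells set to 0, hypoxic-normoxic 8 h at 0 or -0.3) or equal at r = 0 to 0.6. The SAP gives no SD or correlation for nitrate-placebo differences: its 18 mm is a 4 to 6 h change and its correlations are between raw scores.

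**What each test estimates.**
- Main effect: (10 + 10 + 10 + 0)/4 = 7.5 mm, 25% below 10 mm. This needs no SD or correlation. It does need the normoxic effect: at 5 mm there the estimate is 35/4 = 8.75 mm, and at 10 mm there is no dilution.
- Hypoxic contrast: (10 + 10 + 10)/3 = 10 mm.

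**Power, printed correlations.**
- Hypoxic contrast: SD = 18 × √[(3 + 2 × 1.7)/9] = 15.2 mm, so dz = 10/15.2 = 0.66 and power is about 69%.
- Main effect, normoxic SD 18 mm, cross-correlation 0: SD = 18 × √[(4 + 2 × 1.7)/16] = 12.2 mm, so dz = 7.5/12.2 = 0.61 and power is 63%.

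**Power, equal correlation r and SD 18 mm throughout.**
- Hypoxic contrast: SD = 18√[(1 + 2r)/3]. At r = 0.4 this is 13.9 mm, and power is 76%.
- Main effect: SD = 18√[(1 + 3r)/4]. At r = 0.4 this is 13.4 mm, and power is 56%.
- Interaction: noncentrality = n × 75/[324(1 - r)], where 75 = 3 × 2.5² + 7.5². At r = 0.4 this is 16 × 75/194.4 = 6.2, giving 49% on F(3, 45).

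The Greenhouse-Geisser interaction and the cases with unequal SDs were simulated. Power at n = 16:

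| Correlations of differences | Normoxic SD (mm) | Main effect | Interaction (GG) | Hypoxic contrast |
|---|---|---|---|---|
| Printed, cross 0 | 3 | 70% | 49% | 69% |
| Printed, cross 0 | 18 | 63% | 32% | 69% |
| Printed, cross -0.3 | 3 | 70% | 48% | 69% |
| Printed, cross -0.3 | 18 | 67% | 28% | 69% |
| Equal, r = 0 | 18 | 88% | 27% | 95% |
| Equal, r = 0.4 | 18 | 56% | 45% | 76% |
| Equal, r = 0.4 | 9 | 66% | 53% | 76% |
| Equal, r = 0.6 | 18 | 46% | 64% | 68% |
| Equal, r = 0.6 | 9 | 56% | 71% | 68% |

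**The case against.** The strongest reply is that the layout is inferred. The matrix comes from another study, the 2x4 line labels no factor, and normoxic 8 h is correlated only with hypoxic 8 h. That could be a cross-condition correlation at a matched hour and not a fourth level. If all four trial levels are hypoxic, the dilution and the confounding both disappear. This stands as a limit: the point is conditional. But the SAP shows no other four levels and sizes its design on these.

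A second reply is that time points and follow-up comparisons may sit in a protocol not shown. That is fair for silence alone. Here, however, the SAP itself fixes an omnibus ANOVA for headache, and a better-aimed test of the same data is available.

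Third, a reader might infer that the interaction would usually miss a real 10 mm effect. The documents do not support that as a flat statement. It holds under the printed correlations with the sphericity correction, but not at r = 0.4 with a normoxic SD of 9 mm (53%) or at r = 0.6 (64–71%). With equal SDs, the uncorrected interaction passes 80% at r of about 0.7 (82%).

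Fourth, the printed -0.3 might be taken to show that the normoxic score measures something else. One rounded correlation from another study, with no sample size given here, does not prove that.

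Finally, the SAP plans no comparison of an estimate with 10 mm. That figure is a sample-size input only.

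**Conclusion.** The point holds in conditional form. If the four levels are those in the SAP's table, and nitrate has no effect in normoxia, the main effect understates a 10 mm hypoxic effect by a quarter, and the 3-df interaction cannot tell time from oxygen condition. The first is arithmetic; the second follows from the layout.

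The power argument is weaker and depends on assumptions. At n = 16, the corrected interaction has about 28–49% under the printed correlations and 27–71% under equal correlations of 0 to 0.6. The hypoxic contrast has about 69% and 68–95%. At r = 0.6 the interaction can match or slightly exceed the contrast.

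Against the main effect, the contrast gains 0–6 points under the printed correlations and up to about 20 under equal correlations. It would be wrong to read this as a design rescued to 80% power: about 69% under the printed pattern is still short. The case for the contrast is that it estimates the quantity in question and fixes one test in advance.

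**What to change.** 1. State the two factors and the four levels of the headache analysis.
2. Make the headache test one pre-specified 1-df contrast: nitrate minus placebo, averaged over the levels measured in hypoxia only (4, 6 and 8 h if the table is the design), with its 95% CI. If the levels differ from the table, the same rule applies.
3. Take the normoxic 8 h score out of the time factor. Use it only in a secondary contrast: the nitrate-placebo difference at hypoxic 8 h minus that at normoxic 8 h.
4. Report the omnibus interaction as supportive, with a sphericity correction.
5. Do not cite the -0.3 as evidence about what the normoxic score measures.

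The cost is a few sentences, with no new data or participants. The downside is that an effect confined to one hypoxic hour is averaged over three. The Time to exhaustion paragraph already reports in the past tense how many participants completed that component. If headache data had been seen before the contrast was fixed, it must be labelled post hoc.

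### The headache sample size sets a d-type effect of 0.7 against table entries that behave as f-type values, so the stated 80% power at 16 is not supported

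*SAP*

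**What the plan says.** For headache the SAP plans a "2x4 RM ANOVA = Total of 8 repeated measures". Under Effect size it gives "Meaningful difference = 10" and "SD of difference (4-6 h in hypoxia) = 18" (both in mm), hence Cohen's d of 0.55. Under Average correlation it gives "Average correlation = 0.4". The line headed "Conversion to RM ANOVA effect size" divides 0.55 by sqrt(1-0.4) and reports 0.7.

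The sample size table sets each calculated effect directly beside a table entry. The last row (4 measures) pairs 0.7 with Large = 0.49 at a tabulated correlation of 0.3, giving 16. The other rows print 0.57 with 14 and 0.35 with 23, both at a tabulated correlation of 0.5. The closing text states that "16 participants were needed to produce an 80% chance of obtaining statistical significance at the 0.05 level", for a 10 mm difference.

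**The concern.** Cohen's d is the distance between two means in SD units. An omnibus repeated-measures test on several means is usually sized by f, the standard deviation of those means in SD units. For two equal groups of means f = d/2, and in general f depends on the pattern of the means. Dividing by sqrt(1-rho) adjusts for correlation but does not turn d into f. If the table holds f-type entries, 0.7 and 0.49 are on different scales and the match means nothing.

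This look-up is the only support for 80% power on headache, and readers would rely on that figure when interpreting a null result.

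**Working it through.** **Inputs from the SAP.** Difference 10 mm; SD of difference 18 mm; average correlation 0.4; k = 8 measures; alpha 0.05; power 80%; n = 16; printed pairs 0.57/14, 0.35/23 and 0.49/16.

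**Step 1. The SAP's own steps.** 10/18 = 0.556 (printed as 0.55); 0.55/sqrt(0.6) = 0.71 (printed as 0.7).

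**Step 2. Which scale is the table on?** Take the entry as e = f/sqrt(1-rho) and use the multivariate test: df1 = k-1, df2 = n-k+1, noncentrality n·k·e².

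| Entry | Printed N | N found, k = 8 | Power at N | Power at N-1 |
|---|---|---|---|---|
| 0.57 | 14 | 14 | 0.825 | 0.736 |
| 0.35 | 23 | 23 | 0.820 | 0.788 |
| 0.49 | 16 | 16 | 0.830 | 0.766 |

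All three match at the SAP's stated number of measures (k = 7 also fits). If the entries are read as half/half d values, the same test needs 30, 66 and 38. A univariate test on f/sqrt(1-rho) under sphericity needs 7, 16 and 9. A search of 432 combinations (three power levels, k = 2 to 10, both tests, eight readings of the entry) found no other exact match, and no d reading had all three Ns within 2. Multiplying back gives 0.57·sqrt(0.5) = 0.403, 0.35·sqrt(0.5) = 0.247 and 0.49·sqrt(0.7) = 0.410. If 0.7 really were on this scale, the test would need 12 participants and have power 0.99 at 16.

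**Step 3. 10 mm on the table's scale.** Assume four of the eight means lie 10 mm above the other four, with no time or condition effect, so that f = d/2.

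- Following the SAP's use of 18 mm: (0.55/2)/sqrt(0.6) = 0.355.
- Treating 18 mm as an SD of differences, with equal SDs and the printed 4 h to 6 h correlation of 0.4: raw SD = 18/sqrt(2·0.6) = 16.43 mm, and (10/16.43/2)/sqrt(0.6) = 0.393.

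Both are below 0.49. A time or condition effect would raise the omnibus f, but that says nothing about the supplement.

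**Step 4. Omnibus power at n = 16, k = 8.** The univariate test uses df1 = (k-1)·eps, df2 = (k-1)(n-1)·eps and noncentrality eps·n·k·e².

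| Test | e = 0.355 | e = 0.393 |
|---|---|---|
| Multivariate | 0.52 (needs 22) | 0.62 (needs 20) |
| Univariate, sphericity | 0.82 (needs 16) | 0.90 (needs 13) |
| Univariate, eps = 0.7 | 0.71 | 0.80 |
| Univariate, eps = 0.5 | 0.59 | 0.69 |

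**Step 5. Power for a supplement contrast at n = 16.** Read the factor of 2 as supplement and assume an SD of difference of 18 mm at each of the four measures, with correlation r between the four differences. Two-sided paired t-test:

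- 10 mm at all four measures, main effect: SD of the mean difference = 18·sqrt((1+3r)/4) = 11.38, 13.35 or 15.06 mm for r = 0.2, 0.4 or 0.6. Power is 0.91, 0.80 or 0.70.
- A single time point, SD 18 mm: power 0.55.
- 10 mm at the three hypoxic measures and none in normoxia: the main effect averages 30/4 = 7.5 mm, with power 0.69, 0.56 or 0.46. A contrast averaged over the three hypoxic measures, SD = 18·sqrt((1+2r)/3), has power 0.86, 0.76 or 0.68. The 3-df interaction, univariate under sphericity, has power 0.38, 0.49 or 0.68.

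As a check, the same t calculation returns the SAP's 0.8174 for time to exhaustion (30/33, n = 12).

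**The case against.** The strongest reply is that 16 may still be about right. The SAP names a repeated-measures ANOVA, not a multivariate test, and the univariate version gives 0.82 to 0.90 at 16 under sphericity. The 1-df supplement main effect with 10 mm, 18 mm and a correlation of 0.4 gives 0.7996, almost exactly the stated figure. These results stand, and for that reason the point is not that the trial is underpowered. They do not rescue the derivation. The univariate test does not reproduce the SAP's own Ns. The printed correlations run from -0.3 to 0.9, so sphericity cannot be taken for granted. The SAP's 0.4 is a correlation between headache scores, not between supplement differences.

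A second reply is that 0.355 uses the correlation twice, because 18 mm is already an SD of differences. That is fair. The figure follows the SAP's own division by sqrt(1-0.4), and 0.393 suits the printed label better. With 0.393 alone the omnibus range is 0.62 to 0.90, still too wide to support a plain 80%.

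Third, the table is not at hand, so its scale is an inference. That is true, but three exact matches at the stated number of measures, with no d reading close, make it a strong one.

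Finally, the text already describes the time-to-exhaustion component as completed, so a restated power would not change recruitment. It would still correct a figure that readers use.

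**Conclusion.** The concern holds. A d-type 0.7 was set against entries that behave as f/sqrt(1-rho), and the resulting 80% at 16 is not supported by the steps shown. On the table's apparent scale the 10 mm effect is 0.355 to 0.393, against the 0.49 used. Omnibus power at 16 is about 0.52 to 0.90, given the half/half pattern of means with no time or condition effect. For the supplement main effect with 10 mm at all four measures it is 0.70 to 0.91, given an SD of difference of 18 mm at each measure and correlations of 0.6 down to 0.2. True power may lie on either side of 80%. The SAP does not fix the contrast, the pattern of means or the correlation of the supplement differences, so it cannot say which.

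**What to change.** Withdraw the table-based 80% statement and restate power at 16 for a named supplement contrast with its assumptions. Suitable wording: *For the 1-df supplement main effect, with 10 mm at all four measures and an SD of difference of 18 mm at each, power at 16 is 0.91, 0.80 or 0.70 if the four differences correlate 0.2, 0.4 or 0.6.* Add that 18 mm is the SD of the change from 4 to 6 h in hypoxia, so its use for a supplement difference is an assumption. If the effect is expected only in hypoxia, give the figures for that contrast instead.

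If an omnibus figure is kept, put the effect on the f scale, state the pattern of means and the test (multivariate, or univariate with its sphericity assumption), and show the range. The cost is SAP wording and one recalculation, with no extra participants.
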